11.7.6 Solicited Adverse Events

Solicited AEs are defined only in the first 10 days post-vaccination (until study Day 11). All solicited AEs will be reported by the subject in the Subject eDiary and will be recorded on the AE page of the CRF. The same information on severity and causality will be collected for these events as for the unsolicited AEs and they will be coded in the same way. Only those solicited AEs recorded as such on the AE page of the CRF will be included in the main analysis of solicited AEs.

Any solicited adverse events which are reported on the AE page of the CRF but not reported on the eDiary are flagged as recall events. This flag is used in a sensitivity analysis of the solicited AEs.

11.7.6.1 Injection Site Adverse Events

Solicited injection site AEs include injection site pain, tenderness, erythema/redness and induration/swelling. The severity for these AEs will be rated based on the FDA Guidance on Toxicity Grading Scales as described in Table 17.2-1 of the Protocol. Any grade 4 injection site AE should be reported as an SAE and will be reported as Severe (Grade 3) (see Section 11.7.4).

¹ The update regarding the anatomical location of cutaneous pruritus is included to provide further clarification. This information is not included in the current Protocol Version 3.0. However, this definition will be included in all subsequent CSPs.

11.7.6.2 Systemic Adverse Events

Systemic AEs include fever, nausea/vomiting, headache, fatigue, myalgia (muscle pain), arthralgia (joint pain) and rash will be reported in a standardized manner over a period of 10 consecutive days after vaccination.

Severity for systemic AEs will be rated based on the FDA Guidance on Toxicity Grading Scales as described in Table 17.2-2 of the Protocol. Any grade 4 systemic AE should be reported as an SAE and will be reported as Severe (Grade 3) (see Section 11.7.4).

11.7.7 Duration of Adverse Events

Duration of AEs is calculated as (End date – Onset Date) + 1.

If end date for AE is missing, then for the calculation of the duration the date of study completion/early termination/LTFU will be used.

If end date for SAE is missing, then for calculation of duration the date of overall study completion (date last subject had their end of study visit) will be used.

11.7.8 Adverse Events at end of study

Only SAE information should be collected after the end of study for a subject. If a subject has an updated record for an AE that is not an SAE after end of study their AE details will be set to the status that would have been present at end of study.

11.8 Missing Data

All statistical analyses will generally be based on observed values, missing values will not be imputed. Missing severity and causality will be handled as described in Section 11.7.1 and Section 11.7.2 respectively.

In case of > 5% of missing values for the primary immunogenicity analysis, a separate sensitivity analysis will be performed where multiple imputation methods will be applied in order to evaluate the possible impact of missing values on these results.

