18.2 Datasets and Analysis Cohorts

The full analysis set contains all subjects who were randomized and received at least one vaccination. Subjects will be analyzed as randomized.

The safety analysis set contains all subjects who entered into the study and received at least one vaccination. Subjects will be analyzed as treated.

The per protocol (PP) analysis set contains all subjects who were baseline negative for CHIKV antibodies and have received the vaccination and have evaluable immunogenicity data at baseline and the time point for the primary endpoint without a major protocol violation. Examples that may lead to exclusion from the PP population are provided here, further criteria may be defined in the Statistical Analysis Plan (SAP):

- Subject has a known or suspected defect of the immune system that can be expected to influence the immune response to the vaccine, such as subjects with congenital or acquired immunodeficiency, including infection with HIV, status post organ transplantation or immuno-suppressive therapy within 4 weeks prior to Visit 1. Immuno-suppressive therapy is defined as administration of chronic (longer than 14 days) prednisone or equivalent ≥ 0.05 mg/kg/day within 4 weeks prior to study entry, radiation therapy or immunosuppressive cytotoxic drugs/ monoclonal antibodies in the previous 3 years; topical and inhaled steroids are allowed;

- Subject is positive for human immunodeficiency virus (HIV), hepatitis B surface antigen (HBsAg) or hepatitis C virus (HCV);
- Subject has received the wrong (not according to randomization) or no IMP.

These criteria for protocol violations are identified at the time of planning the study. However, during the course of the trial unforeseen events may occur or new scientific knowledge may become available, therefore final decisions on whether a protocol violation could impact on the immune response and thus lead to exclusion from the PP population will be made by the sponsor on a case by case basis in a blinded manner (prior to study unblinding). Sample testing issues may also lead to exclusion from the PP analysis for particular time points.

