18.3 Handling of Missing, Unused, and Spurious Data

All statistical analysis will generally be based on observed values, missing values will not be imputed. In case of >5% of missing values for an immunogenicity comparison involving a statistical test, multiple imputation methods will be applied in order to evaluate the possible impact of missing values on these results.

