9.4.2 Full Analysis Set

The full analysis set (FAS) contains all subjects who were randomized, received the vaccination and have evaluable immunogenicity data at the time point for the primary endpoint. Subjects will be analyzed as randomized.

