9.4.3 Per Protocol Analysis Set

The per protocol (PP) analysis set contains all subjects who were baseline negative for CHIKV antibodies as determined by ELISA assay, have received the vaccination and have evaluable immunogenicity data at baseline and the time point for the primary endpoint without a major protocol deviation. This analysis set will be the primary analysis set for immunogenicity analyses. Subjects will be analyzed in the PP analysis set according to the study arm they have been randomized to.

9.4.4

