9.5.2 Exclusion of Time Points in Per Protocol Analysis

In the PP analysis of immunogenicity, samples with extensive time window deviations will be excluded from the analysis, even if the subject may remain in the PP analysis set. Any scheduled immunogenicity sample collected outside of the visit windows defined in the table below will be excluded from the PP analysis, but analyzed in the FAS.

Due to the fast onset of titer generation after immunization with VLA1553 and the long-term persistence of the titer without significant decrease over one year, the following protocol deviations related to time window deviations are classified as "minor protocol deviations" and do not exclude these subjects from the PP set (except for Visit 3 out of window as defined in section 9.4.3).

Table 9-2 Protocol deviation for immunogenicity samples collected outside of the visit window

Study Part	Visit	Study Day (Visit Window)
	Visit 0 (Screening)	Day -28 to 0 (prior to Visit 1)
	Visit 1	Day 1
	Visit 2	Day 8 (Week 1)
	Visit 3	Day 29 (Month 1)
	Visit 4	Day 85 (Month 3)
	Visit 5	Day 180 (Month 6)

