13.4.2 Primary Immunogenicity Analysis

The primary immunogenicity analysis will be a comparison of the GMTs in the PP analysis set between the VLA1553 Lots 1, 2 and 3 at Day 29 (i.e. 28 days postvaccination) by ANOVA, using the factor Lot as a fixed effect and study center as a covariate. The ANOVA model will be applied to the log-transformed (natural log base e) μ PRNT values of the three Lots and the 95% CIs for the pair-wise ratios of the GMTs will be obtained by taking the anti-log of the resulting 95% CIs for the least square means differences. If these three pairwise 95% CIs for GMT ratios are all between [REDACTED] equivalence between the three commercial batches will be postulated.

The analysis will be performed on the PP analysis set and will be repeated on the Full analysis set.

For the PP analysis set there will be also produced the following graphical outputs:

- a line plot of the GMT at each study timepoint and treatment arm;
- a reverse cumulative distribution plot of the proportion of subjects by treatment arm.

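### With missingness counted inside the SAP's analysis sets, the >5% trigger for the Day 29 multiple-imputation check has essentially nothing to count

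*SAP*

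**What the plan says.** - **Trigger.** SAP 11.8: "In case of > 5% of missing values for the primary immunogenicity analysis, a separate sensitivity analysis will be performed". SAP 13.0 repeats the rule and refers to Section 13.4.3.3 for details. Neither place says over whom the 5% is counted.
- **Sets used.** SAP 13.4.2: "The analysis will be performed on the PP analysis set and will be repeated on the Full analysis set".
- **FAS in the SAP.** SAP 9.4.2: the set "contains all subjects who were randomized, received the vaccination and have evaluable immunogenicity data at the time point for the primary endpoint".
- **Per-protocol (PP) set in the SAP.** SAP 9.4.3: members must be ELISA-negative at baseline, be vaccinated and "have evaluable immunogenicity data at baseline and the time point for the primary endpoint without a major protocol deviation".
- **Late or early Visit 3.** SAP 9.5.2 treats window deviations as minor and keeps the subject in PP, "except for Visit 3 out of window as defined in section 9.4.3".
- **Protocol.** Section 18.2: "The full analysis set contains all subjects who were randomized and received at least one vaccination". Section 18.3: "In case of >5% of missing values for an immunogenicity comparison involving a statistical test, multiple imputation methods will be applied". Section 18.4.1 also repeats the primary analysis on the FAS.
- **Declared changes.** SAP 6.1 covers visit windows, unscheduled visits and the wording of the adverse-event-of-special-interest definition. It mentions neither the FAS nor the imputation rule.

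**The concern.** A rule that reacts to missing primary values needs a population in which such values can be missing. The SAP makes an evaluable Day 29 result a condition of entry to both sets on which the primary analysis is run. Subjects lost before Day 29 are then excluded by definition and never counted as missing. If the trigger were met by some other count, an imputed subject would still belong to neither set.

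At stake is the planned check on whether the lot-consistency conclusion withstands loss of Day 29 data. The SAP also narrows the rule from any tested immunogenicity comparison to the primary one, although ANOVA lot comparisons remain planned at Day 8, Day 85 and Month 6 (SAP 13.4.3.1). In addition, the narrower FAS removes subjects without a Day 29 result from the FAS analyses at those other visits, even if they gave samples then.

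**Working it through.** **1. The plan's own figure.** SAP 8.1 gives 402 randomized subjects (134 per lot), about 90% overall power, SD 0.32 log10, two-sided 5%, and losses of 10% (drop-out), 5% (major deviations) and 2% (baseline positive). The margin is blacked out, so the figure can be reproduced only under an assumption.

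- Evaluable per lot: 134 × (1 − 0.17) = 111.2, so n = 111.
- Power per pair: 2Φ(log10(M) / (0.32 × √(2/n)) − 1.96) − 1. With assumed M = 1.5: 0.1761 / 0.04295 = 4.10, giving 0.968.
- All three pairs: lower bound 1 − 3 × (1 − 0.9676) = 0.90; simulation 0.92.
- Simulated power at other assumed margins: 0.68 (1.4), 0.83 (1.45), 0.985 (1.6), about 1.00 (2.0).

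A margin of 1.5 fits the stated size, but the point does not rest on it. What matters is that the plan itself expects 10% drop-out.

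**2. Missing Day 29 values by denominator, at the planned losses.**

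| Denominator | Expected size | Day 29 values missing | >5% met? |
|---|---|---|---|
| SAP PP | 402 × 0.83 = 334 to 402 × 0.90 × 0.95 × 0.98 = 337 | 0 by definition, apart from sample-testing exclusions (SAP 9.5.1) | No |
| SAP FAS | up to 402 × 0.90 = 362 | 0 by definition | No |
| All randomized (close to the protocol FAS if nearly all are vaccinated) | 402 | 402 × 0.10 = 40.2 | Yes, very probably |

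The last row assumes that all drop-out occurs before Day 29, which the documents do not say.

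**3. Chance of meeting the trigger over all 402.** 5% of 402 is 20.1, so at least 21 missing are needed. P(X ≥ 21) with X ~ Binomial(402, d):

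| True Day 29 loss d | 2% | 3% | 5% | 7% | 10% |
|---|---|---|---|---|---|
| Probability | 0.0001 | 0.011 | 0.45 | 0.94 | 0.9998 |

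The unstated denominator therefore moves the probability from about 0 to about 1 at the plan's own drop-out rate.

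**4. Protocol against SAP.**

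| | Protocol | SAP |
|---|---|---|
| FAS | Randomized and vaccinated (18.2) | Also requires evaluable Day 29 data (9.4.2) |
| PP | Requires Day 29 data (18.2) | Requires Day 29 data (9.4.3) |
| Rule applies to | Any tested immunogenicity comparison (18.3) | Primary analysis only (11.8, 13.0) |

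Under the protocol the rule had no cases to count within PP either, but it could operate on the FAS. The SAP closes that route.

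**5. Imputation details.** Section 13.4.3.3, to which SAP 13.0 refers, is the seroconversion rate. No imputation model appears in the visible SAP.

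**6. Illustrative size of a bias.** Suppose a fraction f of one lot is missing and differs by 1 SD from those observed, with no such loss in the other lots. That lot's GMT moves by a factor of 10^(f × 0.32): 10^0.032 = 1.076 (7.6%) at f = 0.10, and 10^0.048 = 1.117 (11.7%) at f = 0.15. The 10% case uses 0.032/log10(M) of the log margin: 22% at an assumed M of 1.4, 18% at 1.5, 11% at 2.0. Equal informative loss in all lots would give a ratio shift of zero.

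**The case against.** **The denominator is unstated, so the rule might still operate.** The stated aim is to gauge the impact of missing values, which makes most sense if vaccinated subjects without titers are counted. This stands: a reader might infer that the imputation can never run, and the documents do not support that. It does not rescue the text, because the primary analysis exists only on two sets that exclude those subjects. The sponsor is also unblinded for the Part A analysis, so an open denominator could be settled after results are known.

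**The Day 29 FAS result does not change.** This stands. Protocol 18.3 already analyses observed values, so a Day 29 ANOVA on the protocol FAS would omit the same subjects. A reader might infer that the SAP has turned an all-vaccinated analysis into a complete-case one; at Day 29 it was complete-case in both documents.

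**This may not be the only safeguard.** A reader might infer that all protection against informative loss has gone. That cannot be verified: SAP 9.4.4, 13.4.4 and Table 9-1 are blacked out. The visible text also limits Day 29 loss, since unscheduled and early-termination visits falling in the window can stand in for a missed Visit 3 (SAP 11.2).

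**The bias case is demanding.** It needs informative loss in one lot only, in a double-blind trial of lots at one target dose. The documents give no reason to expect this. Imputation under missing-at-random would correct such a bias only as far as the model's covariates explain the loss. This stands; the 7.6% is a stress case, not a forecast.

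**Conclusion.** The point holds as a defect in a stated rule. If missingness is counted within the sets named for the primary analysis, it is about 0% apart from sample-testing exclusions, and the sensitivity analysis would not be triggered at any drop-out rate, including the planned 10%. This rests on that reading of the denominator and, for PP, on SAP 9.5.2 meaning that an out-of-window Visit 3 removes the subject.

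Three things are lost: the planned sensitivity analysis of the primary result, its extension to Day 8, Day 85 and Month 6, and FAS membership at those visits for subjects without Day 29 data. The primary model, the observed-data estimates and the equivalence decision rule are untouched. The documents do not show that the primary result is biased. The SAP should be corrected before the Part A lock, but the matter does not by itself put the lot-consistency conclusion in doubt.

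**What to change.** 1. **SAP 9.4.2:** restore the protocol FAS (all randomized and vaccinated).
2. **SAP 11.8 and 13.0:** count absent or non-evaluable Day 29 titers over all randomized and vaccinated subjects, restricted to ELISA-negative subjects for the PP-like analysis. If more than 5% are missing, run the imputation on that same population.
3. **Model:** impute within lot, because pooling lots would pull the means together and favour equivalence. Include site and the titers available at the time: baseline and Day 8 at Part A, with Day 85 and Month 6 added at Part B. Subjects who left before Day 29 will have little beyond baseline and Day 8, and the report should say so.
4. **Scope:** apply the rule to the tested secondary comparisons at Day 8, Day 85 and Month 6, as protocol 18.3 provides.
5. **Housekeeping:** correct the reference to 13.4.3.3 and list any remaining departure from the protocol in SAP 6.1.

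Cost: SAP wording and one imputation program. No new data are needed, and no protocol amendment, since the change brings the SAP back to the protocol.

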11.9 Handling of Missing or Incomplete Dates

Missing or partial dates will not be imputed, except to determine the timing of AEs or concomitant medications in relation to VLA1553 dosing.

Untoward medical occurrences with missing or partial start dates will be considered AEs unless the partial start date indicates that the event began prior to vaccination with VLA1553, e.g. if the month and/or year are before the month of Visit 1.

Medications with incomplete end dates will only be considered prior if the partial end date indicates that the medication was stopped prior to dosing, e.g. if the month and/or year are before the month of Visit 1. All other medications with missing or incomplete end dates will be considered concomitant.

12.0 Analyses Part A and Part B

No formal interim analysis is planned before completing the part A of the study after day 29.

Nevertheless, data analyses will be provided sequentially by study parts (specified in Table 9-1) and a safety monitoring will be conducted by DSMB as described below.

12.1 Planned Analysis Timepoints

The data analyses will be performed by study parts:

- **Part A analysis** will be performed when all subjects have completed Visit 3 (Day 29) and will comprise immunogenicity and safety data collected to this timepoint.
- **Part A&B analysis** will be performed when all subjects have completed Visit 5 (Month 6) and will comprise all immunogenicity and safety data collected.

The study parts will be analyzed sequentially. Part A will be unblinded once the final subject has completed Visit 3 and database freeze for Part A has occurred (blind will be maintained for study sites). The final Part A&B report will be submitted for licensure.

The analyses to be done at each study part are specified within each section of the statistical methods part of this SAP.

For the Part A analysis, data up to and including Visit 3 (Day 29) or ET if earlier will be kept for all subjects, for the Part B analysis all data will be kept for all subjects. All AEs and concomitant medications with a start date up to and including the date of the cutoff visit for each subject will be included in the analysis. Any record with a start date prior to the cutoff which has a stop date recorded after the cutoff visit for the analysis will be classed as ongoing for the relevant study part.

12.2 Data Safety Monitoring Board

As specified in Section 17.11.1 of the Protocol, an independent Data Safety Monitoring Board (DSMB) will be utilized for this study to address any safety concerns arising during the conduct of the study. The DSMB will review cases of SAEs, AESIs and severe (Grade 3) solicited AEs and provide independent monitoring of safety issues in the subject's interest. In this function the DSMB may mandate changes to the protocol, suggest a protocol amendment and gives recommendations to the sponsor as to whether the study should progress unchanged, or the study requires changes, or the study should be terminated prematurely as the specified in the DSMB charter.

A DSMB charter including a detailed description has been prepared. A separate DSMB table and listing shell document has also been created which will specify the outputs to be produced for review at these meetings.

13.0 Statistical Methods

Unless otherwise noted, categorical variables will be summarized using counts and percentages. Percentages will be rounded to one decimal place, except 100% will be displayed without any decimal places and percentages will not be displayed for zero counts.

Continuous variables will generally be summarized using the number of observations (n), mean, Standard Deviation (SD), median, 25th quartile (Q1), 75th quartile (Q3), minimum and maximum. Summaries of CHIKV-specific NT values will present the number of observations (n), GMT, GSD, median, minimum and maximum. The minimum and maximum values will be displayed to the same level of precision as the raw data, the mean, GSD, median, Q1, and Q3 to a further decimal place, and the SD and GSD to two additional decimal places.

Where relevant, estimates will be presented with 95% two-sided CIs.

All statistical analysis will generally be based on observed values, missing values will not be imputed. In case of >5% of missing values for the primary immunogenicity analysis, a separate sensitivity analysis will be performed where multiple imputation methods will be applied in order to evaluate the possible impact of missing values on these results. Further details are given in Section 13.4.3.3

For the analyses of each study part, all available data will be included, regardless of the subject status during that part of the study. For example, if a subject discontinued the study in part A, they would still be included in any summaries of Part A timepoints in Part B.

Subjects will be always analyzed according to the study arm they have been randomized to. The last column in corresponding summary tables will contain the column TOTAL of all three treatment arms.

Unless otherwise specified, all data collected during the trial will be presented in the subject data listings.

All analyses will use SAS version 9.4 or higher.

13.1 Subject Disposition

The number and percentage of subjects screened, randomized and vaccinated in the study will be presented, together with the number and percentage of subjects who withdrew from the study prematurely during each part and a breakdown of the corresponding reasons for early termination and discontinuation.

Tabulations of the number and percentage of subjects included in each analysis set will be provided. Reasons for exclusion from each analysis set will not be tabulated, but will be listed.

The number and percentage of subjects in the study at each timepoint will also be presented.

A tabulation of the number and percentage of subjects randomized at each center will be presented.

13.2 Demographic and Baseline Characteristics

Demographic characteristics to be summarized will include gender, ethnicity, race, age at screening (years), height (cm), weight (kg) and body mass index (BMI) (kg/m²).

Medical history will be summarized by system organ class (SOC) and PT using the current version of MedDRA.

A separate summary of vaccination history at baseline will be provided.

All demographic and baseline summaries will be provided on the Safety analysis set. Additionally the summary of demographic characteristics will be presented for the PP analysis set. All demographic and baseline data will be listed.

